3.1.1.2. Systemic Events (Systemic Event Symptoms and Fever)

The systemic events assessed and recorded in the e-diary are fever, fatigue/tiredness, headache, chills, vomiting, diarrhea, new or worsened muscle pain, and new or worsened joint pain within 7 days after vaccination. The derivations for systemic events will be handled similarly to the way local reactions are handled for presence of event, severity level, duration, and onset day (see [Section 3.1.1.1](#)).

The systemic events will be assessed by the participant as mild, moderate, or severe according to the grading scale in Table 6.

If a Grade 3 systemic event is reported in the reactogenicity e-diary, a telephone contact should occur to ascertain further details and determine whether a site visit is clinically indicated. Only an investigator or medically qualified person is able to classify a participant's systemic event as Grade 4. If a participant experiences a confirmed Grade 4 systemic event, the investigator must immediately notify the sponsor.

Table 6. Systemic Event Grading Scale

Systemic Event	Mild (Grade 1)	Moderate (Grade 2)	Severe (Grade 3)	Potentially Life-Threatening (Grade 4)
Vomiting	1-2 times in 24 hours	>2 times in 24 hours	Requires IV hydration	Emergency room visit or hospitalization for hypotensive shock
Diarrhea	2 to 3 loose stools in 24 hours	4 to 5 loose stools in 24 hours	6 or more loose stools in 24 hours	Emergency room visit or hospitalization for severe diarrhea
Headache	Does not interfere with activity	Some interference with activity	Prevents daily routine activity	Emergency room visit or hospitalization for severe headache
Fatigue/tiredness	Does not interfere with activity	Some interference with activity	Prevents daily routine activity	Emergency room visit or hospitalization for severe fatigue
Chills	Does not interfere with activity	Some interference with activity	Prevents daily routine activity	Emergency room visit or hospitalization for severe chills
New or worsened muscle pain	Does not interfere with activity	Some interference with activity	Prevents daily routine activity	Emergency room visit or hospitalization for severe new or worsened muscle pain
New or worsened joint pain	Does not interfere with activity	Some interference with activity	Prevents daily routine activity	Emergency room visit or hospitalization for severe new or worsened joint pain

Abbreviation: IV = intravenous.

During the 7 days following the vaccination, potential COVID-19 symptoms that overlap with solicited systemic events (ie, fever, chills, new or worsened muscle pain, diarrhea, vomiting) should be assessed by the investigator.

If, in the investigator's opinion, the symptoms are considered more likely to be vaccine reactogenicity, but a participant is required to demonstrate that he or she is SARS-CoV-2-negative, a local SARS-CoV-2 test may be performed: if positive, the symptoms should be recorded as an AE rather than as systemic events in the reactogenicity e-diary.

Potential COVID-19 symptoms that do not overlap with systemic events should be reported as AEs as per Section 8.3 of the protocol.

Oral temperature will be collected in the reactogenicity e-diary in the evening daily during the reactogenicity e-diary reporting period (7 days after each vaccination) and at any time during the 7 days that fever is suspected. Fever is defined as an oral temperature of $\geq 38.0^{\circ}\text{C}$ ($\geq 100.4^{\circ}\text{F}$). The highest temperature for each day will be recorded in the e-diary.

Temperatures will be measured and recorded to 1 decimal place. Temperatures recorded in degrees Fahrenheit will be programmatically converted to degrees Celsius first for reporting. Temperatures $<35.0^{\circ}\text{C}$ and $>42.0^{\circ}\text{C}$ will be excluded from the analysis. Fever will be grouped into ranges for the analysis according to Table 7.

If a fever of $\geq 39.0^{\circ}\text{C}$ ($\geq 102.1^{\circ}\text{F}$) is reported in the reactogenicity e-diary, a telephone contact should occur to ascertain further details and determine whether a site visit is clinically indicated. Only an investigator or medically qualified person is able to confirm a participant's fever as $>40.0^{\circ}\text{C}$ ($>104.0^{\circ}\text{F}$). If a participant experiences a confirmed fever $>40.0^{\circ}\text{C}$ ($>104.0^{\circ}\text{F}$), the investigator must immediately notify the sponsor.

Table 7. Scale for Fever

$\geq 38.0\text{-}38.4^{\circ}\text{C}$ ($100.4\text{-}101.1^{\circ}\text{F}$)
$>38.4\text{-}38.9^{\circ}\text{C}$ ($101.2\text{-}102.0^{\circ}\text{F}$)
$>38.9\text{-}40.0^{\circ}\text{C}$ ($102.1\text{-}104.0^{\circ}\text{F}$)
$>40.0^{\circ}\text{C}$ ($>104.0^{\circ}\text{F}$)

3.1.1.3. Use of Antipyretic Medication

The use of antipyretic medication to treat symptoms associated with study intervention administration will also be recorded in the reactogenicity e-diary daily during the reporting period (7 days after each vaccination). For the use of antipyretic medication within 7 days after vaccination, the following endpoints and variables will be derived for analysis following the same rules as for local reactions (see [Section 3.1.1.1](#)), where applicable.

- Presence (yes or no) of use of antipyretic medication on each day (7 days after vaccination).
- Presence (yes or no) of use of antipyretic medication on any day (within 7 days after vaccination).

- Duration (first to last day reported) of use of antipyretic medication.
- Onset day of use of antipyretic medication.

The use of antipyretic medication will be summarized and included in the systemic event summary tables but will not be considered a systemic event.

3.1.1.4. Adverse Events

AEs will be assessed from the time of informed consent through 1 month after the study vaccination. In addition, any AEs occurring up to 48 hours after any subsequent blood draw must be recorded on the CRF. AEs will be categorized according to MedDRA terms. Missing AE start dates will be imputed following the Pfizer data standard rules as described in [Section 5.3](#).

The primary safety endpoint “AEs from the study vaccination through 1 month after the study vaccination” and other AE endpoints will be summarized by system organ class and preferred term.

These primary endpoints will be supported by summaries and/or listings of related AEs, severe AEs, immediate AEs (within the first 30 minutes after each vaccination), and AESIs (defined in Section 8.3.8 of the protocol).

3.1.1.5. Serious Adverse Events

SAEs will also be collected from the time of informed consent through 6 months after the study vaccination. SAEs will be categorized according to MedDRA terms.

The safety endpoint “SAEs from the study vaccination through 6 months after the vaccination” will be summarized by system organ class and preferred term. Additionally, SAEs will be listed.

3.1.2. Primary Immunogenicity Endpoints

- SARS-CoV-2 reference-strain–neutralizing titers at each time point.
- SARS-CoV-2 Omicron-neutralizing titers at each time point.

3.2. Secondary Endpoint(s)

Not applicable.

3.3. Other Endpoint(s)

3.3.1. Exploratory Endpoints

- SARS-CoV-2-neutralizing titers for any VOCs not already specified.
- T-cell (by ELISPOT) and B-cell characterization.
- RBD-binding IgG.
- RBD-binding IgA.
- Confirmed COVID-19 cases.
- Confirmed severe COVID-19 cases.
- Strain sequencing of COVID-19 cases.

3.4. Baseline Variables

Measurements or samples collected prior to the study vaccination are considered the baseline data for the assessments.

3.4.1. Demographics, Medical History, and Physical Examination

The demographic variables will be collected, including date of birth, sex (male or female), race (Black or African American, American Indian or Alaskan native, Asian, Native Hawaiian or other Pacific Islander, White, multiracial, and not reported), and racial designation and ethnicity (Hispanic/Latino, non-Hispanic/non-Latino, and not reported). In cases where more than 1 category is selected for race, the participant would be counted under the category “multiracial” for analysis.

Age at the time of the study vaccination (in years) will be derived based on the participant’s birthday. For example, if the vaccination day is 1 day before the participant’s 65th birthday, the participant is considered to be 64 years old.

Medical history will be collected and categorized according to the current version (at the time of reporting) of MedDRA.

If the clinical assessment indicates that a physical examination is necessary to comprehensively evaluate the participant at Visit 701, a physical examination will be performed and any findings will be recorded in the source documents and, if clinically significant, on the medical history CRF.

3.4.2. E-Diary Transmission

An e-diary will be considered transmitted if any data for the local reactions, systemic events, or use of antipyretic medication are present for any day. If all data are missing for all the items on the e-diary for all 7 days after vaccination, the e-diary will be considered not transmitted.

3.4.3. Prior/Concomitant Vaccines and Concomitant Medications

The following concomitant medications and vaccinations will be recorded in the CRF:

- All vaccinations received from 28 days prior to study enrollment until 28 days following administration of the last study intervention.
- Prohibited medications listed in the protocol, Section 6.8.1, will be recorded to include start and stop dates, name of the medication, dose, unit, route, and frequency.

Prior and concomitant vaccines and concomitant medications will be coded using the WHO Drug Dictionary.

3.5. Safety Endpoints

Local reactions, systemic events, AEs, and SAEs are described in the Primary Safety Endpoints section ([Section 3.1.1](#)).

4. ANALYSIS SETS (POPULATIONS FOR ANALYSIS)

Analysis populations are defined for the statistical analysis of safety and immunogenicity results in Table 8. Data for all participants will be assessed to determine if participants meet the criteria for inclusion in each analysis population prior to unblinding and releasing the database, and classifications will be documented per standard operating procedures.

Table 8. Description of the Analysis Sets

Population	Description
Enrolled	All participants who have a signed ICD.
Randomized/assigned	All participants who are assigned a randomization number in the IWR system.
Evaluable immunogenicity	All eligible randomized/assigned participants who receive the study intervention to which they are randomized or assigned, have a valid and determinate immunogenicity result from the blood sample collected within 28-42 days after the study vaccination, and have no other important protocol deviations as determined by the clinician.
All-available immunogenicity	All randomized/assigned participants who receive the study intervention with a valid and determinate immunogenicity result after vaccination.
Safety	All participants who receive the study intervention.

Important protocol deviations will be determined by the medical monitor. An important protocol deviation is a protocol deviation that, in the opinion of the sponsor's clinician, would materially affect assessment of immunogenicity, eg, participant receipt of a prohibited vaccine or medication that might affect immune response or a medication error with suspected decrease in potency of the vaccine. The sponsor's medical monitor will identify those participants with important protocol deviations that result in exclusion from analysis populations before any unblinded analysis is carried out.

The safety analyses are based on the safety population. Participants will be summarized by vaccine group according to the study interventions they received. Missing reactogenicity e-diary data will not be imputed; missing AE dates will be handled according to the Pfizer safety rules.

For all the immunogenicity endpoints, the analysis will be based on the evaluable immunogenicity population. An additional analysis may be performed based on the all-available immunogenicity population if there is a $\geq 10\%$ difference in sample size between the all-available immunogenicity population and the evaluable immunogenicity population. Participants will be summarized according to the vaccine group to which they were randomized. Missing serology data will not be imputed.

5. GENERAL METHODOLOGY AND CONVENTIONS

Methodology for summary and statistical analyses of the data collected in this study is described here. The SAP may modify what is outlined in the protocol where appropriate; however, any major modifications of the primary endpoint definitions or their analyses will also be reflected in a protocol amendment.

The sponsor will be unblinded to the study intervention allocation for the sentinel cohort. For the expanded-enrollment part of the study, the majority of sponsor/Pfizer staff will be blinded to study intervention allocation. All laboratory testing personnel performing serology assays will remain blinded to study intervention assigned/received throughout the testing. Further details can be found in Section 10.12.6.2.2. of the protocol. The timing for statistical analysis is specified in [Section 7.3](#).

5.1. Hypotheses and Decision Rules

All objectives in this substudy are descriptive. No hypothesis testing is planned.

5.2. General Methods

CIs for all endpoints in the statistical analysis will be presented as 2-sided at the 95% level unless otherwise specified.

5.2.1. Analyses for Binary Data

Descriptive statistics for categorical variables (eg, proportions) are the percentage (%), the numerator (n) and the denominator (N) used in the percentage calculation, and the 95% CIs where applicable.

The exact 95% CI for binary endpoints for each group will be computed using the F distribution (Clopper-Pearson method).¹ The 95% CI for the between-group difference for binary endpoints will be calculated using the Miettinen and Nurminen method.²

5.2.2. Analyses for Continuous Data

Unless otherwise stated, descriptive statistics for continuous variables are n, mean, median, standard deviation, minimum, and maximum.

5.2.2.1. Geometric Means

The geometric means will be calculated as the mean of the assay results after making the logarithm transformation and then exponentiating the mean to express results on the original scale. Two-sided 95% CIs will be obtained by taking log transforms of assay results, calculating the 95% CI with reference to Student's t-distribution, and then exponentiating the confidence limits.

5.2.2.2. Geometric Mean Fold Rises

GMFRs are defined as ratios of the results after vaccination to the results before vaccination. GMFRs are limited to participants with nonmissing values at both time points.

GMFRs will be calculated as the mean of the difference of logarithmically transformed assay results (later time point minus earlier time point) and exponentiating the mean. The associated 2-sided 95% CIs will be obtained by constructing CIs using Student's t-distribution for the mean difference on the logarithm scale and exponentiating the confidence limits.

5.2.2.3. Geometric Mean Ratios

The relative difference in antibody levels between different vaccine groups, using the BNT162b2 30- μ g group as the reference, will be estimated using an ANCOVA model. For each time point after the baseline, log-antibody levels will be modeled using linear regression with the vaccine group as the exposure and the baseline antibody levels as a covariate. The GMR and associated 95% CI will be calculated by exponentiating the difference in least-squares means and the corresponding CIs.

5.2.2.4. Reverse Cumulative Distribution Curves

Empirical RCDCs will plot proportions of participants with values equal to or exceeding a specified assay value versus the indicated assay value, for all observed assay values. Data points will be joined by a step function with data points on the left side of the step.

5.3. Methods to Manage Missing Data

A partial AE start date (missing day or missing both month and day) will be imputed by assigning the earliest possible start date using all available information, such as the stop date of the AE and the vaccination date(s) from the same participant, following the Pfizer standard for handling incomplete AE start date. A complete missing start date for an AE is not allowed in the data collection.

Missing serology results will not be imputed. Immunogenicity results that are below the LLOQ, denoted as BLQ, will be set to $0.5 \times \text{LLOQ}$ in the analysis; this may be adjusted once additional data on the assay characteristics become available.

No additional imputation will be applied to other missing data.

6. ANALYSES AND SUMMARIES

6.1. Primary Endpoint(s)

6.1.1. Primary Safety Endpoints

6.1.1.1. Local Reactions

6.1.1.1.1. Main Analysis

- Estimand: The percentage of participants reporting local reactions (redness, swelling, and pain at the injection site) for up to 7 days after the study vaccination ([Section 2.2](#)).
- Analysis set: Safety population ([Section 4](#)).
- Analysis time point: Up to 7 days after the study vaccination.
- Analysis methodology: Descriptive statistics ([Section 5.2.1](#)).
- Intercurrent events and missing data: The participants without any e-diary data throughout the 7 days after vaccination will be excluded from the analysis; missing values will not be imputed.
- Reporting results: Descriptive statistics for each and any local reaction after the study vaccination in each vaccine group will be presented by maximum severity and cumulatively across severity levels. Descriptive summary statistics will include counts and percentages of participants with the indicated endpoint and the associated 2-sided Clopper-Pearson 95% CIs.

6.1.1.2. Supplemental Analyses

To support the assessment of local reactions, the following endpoints (as defined in [Section 3.1.1.1](#)) will be summarized with the same analysis time point and analysis population as above and the appropriate analysis methodology and reporting results:

- Duration (days) of each local reaction after the study vaccination.
- Onset day of each local reaction after the study vaccination.

These continuous endpoints will be summarized by displaying n, mean, median, standard deviation, minimum, and maximum by vaccine group.

Figures:

Bar charts with the proportions of participants for each local reaction throughout 7 days after the study vaccination will be plotted by vaccine group. The bars will be divided into severity categories to highlight the proportions of participants by maximum severity.

6.1.1.2. Systemic Events

6.1.1.2.1. Main Analysis

- Estimand: The percentage of participants reporting systemic events (fever, fatigue, headache, chills, vomiting, diarrhea, new or worsened muscle pain, and new or worsened joint pain) for up to 7 days after the study vaccination ([Section 2.2](#)).
- Analysis set: Safety population ([Section 4](#)).
- Analysis time point: Up to 7 days after the study vaccination.
- Analysis methodology: Descriptive statistics ([Section 5.2.1](#)).
- Intercurrent events and missing data: The participants without any e-diary data throughout the 7 days after vaccination will be excluded from the analysis; missing values will not be imputed.
- Reporting results: Descriptive statistics for each systemic event after the study vaccination in each vaccine group will be presented by maximum severity and cumulatively across severity levels. Descriptive summary statistics will include counts and percentages of participants with the indicated endpoint and the associated 2-sided Clopper-Pearson 95% CIs.

6.1.1.2.2. Supplemental Analyses

The following endpoints for assessment of systemic events will be summarized similarly to the assessment of local reactions:

- Duration of each systemic event after the study vaccination.
- Onset day of each systemic event after the study vaccination.

These continuous endpoints will be summarized by displaying n, mean, median, standard deviation, minimum, and maximum for the dose by vaccine group.

The use of antipyretic medication (see [Section 3.1.1.3](#)) will be summarized similarly to systemic events, except that there is no severity level associated with the use of antipyretic medication.

Figures:

Bar charts with the proportions of participants reporting each systemic event throughout 7 days will be plotted for each vaccine group. The bars will be divided into severity categories to highlight the proportions of participants by maximum severity.

6.1.1.3. Adverse Events

6.1.1.3.1. Main Analysis

- Estimand: The percentage of participants reporting AEs from the study vaccination through 1 month after the study vaccination ([Section 2.2](#)).
- Analysis set: Safety population ([Section 4](#)).
- Analysis time point: From the study vaccination through 1 month after the study vaccination.
- Analysis methodology: Descriptive statistics ([Section 5.2.1](#) and [Section 3.1.1.4](#)).
- Intercurrent events and missing data: Missing data will not be imputed except for partial AE start dates ([Section 5.3](#)).
- Reporting results: Counts, percentages, and the associated 2-sided Clopper-Pearson 95% CIs of AEs within 1 month after the study vaccination will be provided for each vaccine group.

6.1.1.3.2. Supplemental Analyses

AEs from the study vaccination through 7 days after the study vaccination will be summarized similarly for the IRC and at the corresponding planned analysis timing described in [Section 7.3](#).

Related AEs, severe AEs, immediate AEs (within the first 30 minutes after the study vaccination), and AESIs (defined in Section 8.3.8 of the protocol) will also be summarized by vaccine group.

All AEs after informed consent and prior to the first vaccination will not be included in the analyses but will be in the listing.

6.1.1.4. Serious Adverse Events

6.1.1.4.1. Main Analyses

- Estimand: The percentage of participants reporting SAEs from the study vaccination through 6 months after the study vaccination ([Section 2.2](#)).
- Analysis set: Safety population ([Section 4](#)).
- Analysis time point: From the study vaccination through 6 months after the study vaccination.
- Analysis methodology: Descriptive statistics ([Section 5.2.1](#)).
- Intercurrent events and missing data: Missing data will not be imputed except for partial AE start dates ([Section 5.3](#)).
- Reporting results: Counts, percentages, and the associated Clopper-Pearson 95% CIs of SAEs from the study vaccination (received in this study) through 6 months after the study vaccination will be provided for each vaccine group.

6.1.1.4.2. Supplemental Analyses

SAEs from the study vaccination through 7 days after the study vaccination will be summarized similarly for the IRC and at the corresponding planned analysis timing described in [Section 7.3](#).

6.1.2. Primary Immunogenicity Endpoints

6.1.2.1. Primary Immunogenicity Endpoints

6.1.2.1.1. Main Analyses

- Estimands:
 1. GMTs of SARS-CoV-2 Omicron- and reference-strain–neutralizing titers at each time point for each vaccine group.
 2. GMFRs of SARS-CoV-2 Omicron- or reference-strain–neutralizing titers from before the study vaccination to each subsequent time point after the study vaccination for each vaccine group.
 3. Percentages of participants with seroresponse to Omicron or the reference strain at each time point for each vaccine group.
 4. GMRs of SARS-CoV-2 Omicron- and reference-strain–neutralizing titers at each time point after the study vaccination between different vaccine groups.
- Analysis sets: Evaluable immunogenicity population, all-available immunogenicity population (as applicable) ([Section 4](#)).
- Analysis time points: Before the study vaccination and each subsequent time point after the study vaccination.
- Analysis methodology: GMTs and the associated 2-sided 95% CIs will be calculated using the statistical methods described in [Section 5.2.2.1](#). The GMFRs and the associated 2-sided 95% CIs from before the study vaccination to each subsequent time point after vaccination will be provided using the statistical methods described in [Section 5.2.2.2](#). The percentages of participants with seroresponse at each time point and the associated Clopper-Pearson 95% CI for each group will be provided. GMRs and the associated 2-sided 95% CIs will be calculated using the statistical methods described in [Section 5.2.2.3](#).
- Intercurrent events and missing data: Serology data deemed unevaluable because of noncompliance with the key protocol criteria will be excluded. Missing data will not be imputed.

- Reporting results: GMTs at each time point and GMFRs of SARS-CoV-2 Omicron- or reference-strain–neutralizing titers from before the study vaccination to each subsequent time point after vaccination, along with the associated 2-sided 95% CIs, will be provided for each vaccine group. The percentages of participants with seroresponse at each time point and the associated Clopper-Pearson 95% CIs will be provided for each vaccine group. Model-based GMRs at each time point after the study vaccination, along with the associated 2-sided 95% CIs, will be provided for each vaccine group (using the BNT162b2 30- μ g group as the reference).

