2.2. Study Objectives, Endpoints, and Estimands

The estimands corresponding to each primary, secondary, and exploratory objective in Study C4591031 – Substudy F are described in Table 2 below.

In the primary safety objective evaluations, missing AE start dates will be imputed according to Pfizer safety rules ([Section 5.3](#)). No other missing information (eg, missing e-diary data) will be imputed in the safety analysis.

The estimands to evaluate the immunogenicity objective are based on the evaluable immunogenicity population (see [Section 4](#) for definition). These estimands estimate vaccine effect in the hypothetical setting where participants follow the study schedules and protocol requirements as directed. Missing serology results will not be imputed. Immunogenicity results that are below the LLOQ, denoted as BLQ, will be set to $0.5 \times \text{LLOQ}$ in the analysis; this may be adjusted once additional data on the assay characteristics become available.

Table 2. List of Primary and Exploratory Objectives, Endpoints, and Estimands

Objectives	Estimands	Endpoints
Primary Safety		
To describe the safety and tolerability profile of BNT162b2 (30 µg or 60 µg), BNT162b2 OMI (30 µg or 60 µg), and a combination of BNT162b2 and BNT162b2 OMI (30 µg or 60 µg) given as the fourth dose to BNT162b2-experienced participants	
In participants receiving at least 1 dose of study intervention, the percentage of participants reporting:
 
 Local reactions for up to 7 days following the study vaccination Systemic events for up to 7 days following the study vaccination AEs from the study vaccination through 1 month after the study vaccination SAEs from the study vaccination through 6 months after the study vaccination 	
 Local reactions (pain at the injection site, redness, and swelling) Systemic events (fever, fatigue, headache, chills, vomiting, diarrhea, new or worsened muscle pain, and new or worsened joint pain) AEs SAEs
Primary Immunogenicity		

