6.2.1.3. COVID-19 Cases

Confirmed COVID-19 cases, confirmed severe COVID-19 cases, and strain sequencing of the COVID-19 cases will be summarized for each vaccine group.

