6.3. Subset Analyses

No subset analyses will be conducted.

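### The SAP states no strategy for SARS-CoV-2 infection after the study vaccination in the primary titer analyses, so late GMTs, GMFRs and seroresponse rates can include infection-induced antibody.

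*SAP*

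**What the plan says.** SAP Section 2.2 sets the target of the immunogenicity estimands: "These estimands estimate vaccine effect in the hypothetical setting where participants follow the study schedules and protocol requirements as directed". Section 6.1.2.1.1 gives the analysis time points for the primary titers as "Before the study vaccination and each subsequent time point after the study vaccination", and Section 7.3 schedules immunogenicity analyses at 1, 3 and about 6 months.

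Three places decide which titers count:

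- **Section 6.1.2.1.1**, intercurrent events: "Serology data deemed unevaluable because of noncompliance with the key protocol criteria will be excluded". Missing data are not imputed.
- **Section 4**, evaluable immunogenicity population: the assigned vaccine, a valid result from a "blood sample collected within 28-42 days after the study vaccination", and the requirement that participants "have no other important protocol deviations as determined by the clinician". The examples of such deviations are "participant receipt of a prohibited vaccine or medication that might affect immune response" and a medication error with suspected loss of potency.
- **Section 5.2.2.3**, the GMR model: vaccine group and baseline antibody level only.

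Infection appears separately, as an exploratory endpoint in Section 6.2.1.3: "Confirmed COVID-19 cases, confirmed severe COVID-19 cases, and strain sequencing of the COVID-19 cases will be summarized for each vaccine group". Section 6.3 adds: "No subset analyses will be conducted".

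**The concern.** Infection is an antigen exposure that can raise neutralizing titers. A sample drawn after it measures vaccine plus infection. Section 4 treats a prohibited vaccine as grounds for exclusion because it might affect the immune response, yet no rule addresses infection, which can do the same. No treatment-policy strategy is declared that would explain keeping those titers.

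At stake is what the 3- and 6-month primary results can support. A late GMT, GMFR or seroresponse rate may read as persistence of the vaccine response when part of it comes from infection. The 1-month sample can be affected too, but over a shorter exposure. Timing also matters: the sponsor is unblinded to the sentinel cohort (Section 5), and an unblinded team analyses the expanded cohort while the study is ongoing (Section 7.3). A rule written after the 1- or 3-month results would be post hoc.

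**Working it through.** **Does any rule reach a post-infection titer?** Take a participant who receives the assigned vaccine, gives a valid 28-42 day sample, is infected in month 2 and is sampled at months 3 and 6.

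- Noncompliance (Section 6.1.2.1.1): no.
- Important deviation (Section 4): it must first be a protocol deviation, and infection is not one.
- Sampling window (Section 4): met, and no evaluability criterion is tied to a later visit.
- Model (Section 5.2.2.3): no infection term.
- All-available analysis (Section 4): optional, and it would not remove these titers either.

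Both late titers stay in every primary summary.

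**Inputs from the SAP.** Six groups of 5 sentinel plus 25 expanded participants (Section 2.3): 6 × (5 + 25) = 180, which reproduces the stated total of about 180, with 30 per group. No attack rate, infection boost or titer SD is given.

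**Assumptions.** p is the share of a group infected before the draw, k the geometric mean boost in those infected, and the log10 titer SD is 0.4 without infection.

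**1. GMT and GMFR.** The mean log titer rises by p × log k, so both are multiplied by k^p.

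| p | k = 4 | k = 8 | k = 10 |
|---|---|---|---|
| 10% | 1.15 | 1.23 | 1.26 |
| 20% | 1.32 | 1.52 | 1.58 |
| 30% | 1.52 | 1.87 | 2.00 |

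At p = 10%, the chance of at least one infected participant in a group of 30 is 1 − 0.9^30 = 0.96.

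**2. Seroresponse.** The rate becomes (1 − p)s + p × s_inf. With s = 30% and an assumed 90% among the infected, it becomes 36%, 42% and 48% at p = 10%, 20% and 30%.

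**3. GMR.** The multiplier is k^(p1 − p0), where group 0 is the BNT162b2 30 µg reference.

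- Equal risk: k^0 = 1, so no bias on average.
- Illustration, p0 = 25% and p1 = 10%: k^(−0.15) = 0.81, 0.73 and 0.71 for k = 4, 8 and 10.
- Chance alone, p = 20% in both groups: the SD of the difference in shares is √(2 × 0.2 × 0.8/30) = 0.103. With k = 8 the 95% range of the multiplier is 8^(±1.96 × 0.103), about 0.66 to 1.52.

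**4. Precision.** At p = 20% and k = 8, SD = √(0.4² + 0.2 × 0.8 × (log10 8)²) = 0.54. Since 0.54/0.4 = 1.35, the interval is about 35% wider on the log scale than with no infection. Dropping the infected 20% costs 1/√0.8 = 1.12, or 12%. The fair comparison is 1.35/1.12 = 1.20, so keeping these titers gives an interval about 20% wider than excluding them.

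**The case against.** The strongest reply is that the SAP does not contradict itself. The hypothetical in Section 2.2 is adherence to schedule and protocol, not freedom from infection, so keeping post-infection titers is compatible with it. This stands: the fault is an undeclared strategy, not an inconsistency.

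A reader might infer three stronger things that the text does not support.

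- **That contamination must differ between arms and so biases the GMRs.** All six arms are active fourth doses in people with three prior doses, and nothing in the SAP shows different infection risk.
- **That Section 6.3 closes off any remedy.** Removing post-infection samples is a data-handling rule rather than a subgroup analysis, Section 7.3 allows additional analyses for regulatory purposes, and cases are reported by group.
- **That exclusion should become the primary analysis.** If infection depends on protection, exclusion selectively removes less-protected participants and can itself bias late GMRs. Undetected infections also remain.

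The protocol, which is not at hand, may define the key criteria more widely, and Section 4 leaves important deviations to clinical judgement. Even so, the SAP's own intercurrent-event line does not mention infection, and infection is not naturally a deviation.

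**Conclusion.** The concern holds as a gap in the plan. No SAP rule removes, separates or declares the treatment of titers drawn after infection. Late GMTs, GMFRs and seroresponse rates are raised by any boosting infection, in whichever group it occurs. The size cannot be fixed from the documents; across the assumed 10% to 30% infected and 4- to 10-fold boost it is about 1.15 to 2.0 times for GMT and GMFR. For the GMRs the supportable claim is narrower: wider intervals, and distortion only where infection differs between groups through protection or chance.

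All objectives are descriptive and no hypothesis testing is planned (Section 5.1), so type I error, power and decision rules are untouched. The harm is to interpretation of the 3- and 6-month estimates. This should be fixed, but it does not invalidate the plan.

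**What to change.** In Section 6.1.2.1.1, name SARS-CoV-2 infection after the study vaccination as an intercurrent event. State that GMT, GMFR, seroresponse and GMR will be shown at each time point in the same evaluable immunogenicity population in two ways:

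1. with all titers;
2. without titers from samples drawn on or after the onset of a confirmed COVID-19 case, or of other collected evidence of infection, which the SAP should specify. Earlier samples from that participant stay in.

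Do not use the all-available population as the unexcluded comparison. It also drops the 28-42 day and deviation criteria, so a difference could not be attributed to infection. Add a sentence that Section 6.3 does not preclude this analysis, and settle the rule before group results are seen.

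The cost is SAP wording and one extra set of tables from data already collected. The exclusion analysis has fewer late samples, rests on a post-randomization exclusion that can bias late GMRs, and misses undetected infections. The two results must therefore be read together.
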